### **7.6.16 Non-Protocol Medical Procedures**

Non-protocol medical procedures will be listed by subject.

**7.6.18 Pregnancy**

[figure not shown]
Not applicable. This study allows only for women not of childbearing potential.

[figure not shown]
**7.6.19 Adverse Events by Subgroup (Randomized Phase only)**

[figure not shown]
Overall summary of any AEs and drug-related AEs by worst CTC grade (any grade, grade 3-4, grade 5) presented by SOC/PT and for each treatment group for the following subgroups:

[figure not shown]
- Sex (Male vs. Female)
- Race
- Age (< 65 vs. 65 - < 75 vs. 75 - < 85 vs. ≥ 85 vs. ≥ 75 vs. ≥ 65)
- Region (US/Canada, Europe, Rest of the World)

These analyses will be conducted using the 30-day safety window only.

### **7.10 Analyses at the time of the decision for the dose level to be evaluated in the randomized phase.**

At the time of the analysis for the selection of the dose to be evaluated in the randomized phase of the study (see paragraph Schedule of Analyses in [Section 1](#) for the timing of the analysis), the following analyses will be produced using all available data from the safety run-in phase:

- Summary and listing of the relevant protocol deviations during the safety run-in phase
- Summaries and listings of subject disposition for each study period of the safety run-in phase
- Summaries of demographic and baseline disease characteristics
- Listing of medical history
- Summaries and listings of prior therapy agents
- Listing of physical examinations
- Summaries and listings of administration of study therapy
- Summaries of modifications of study therapy
- Summary and listing of concomitant medications
- Summary and listing of dose-limiting toxicities
- Summary and listing of deaths
- Summaries of SAEs, drug-related SAEs, AEs leading to discontinuation, drug-related AEs leading to discontinuation, AEs leading to dose delay/reduction, drug-related AEs leading to dose delay/reduction, AEs, drug-related AEs, any select AEs, any non-endocrine and endocrine IMAEs where immune modulating medication was initiated, OEOSI, AEs of Interstitial Lung

Disease (ILD), pneumonitis and immune-mediated pneumonitis. All these summaries will be presented by worst CTC grade (any grade, grade 3-4, grade 5) using the 30 days safety window.

- Listing of AEs
- Summary and listing of marked laboratory abnormalities in both US and SI units using the 30 days safety window.

At the time of this analysis, the safety run-in phase will not be completed. A clinical study report may not be prepared at this point. For the analyses for the clinical study report, the full set of analyses for the safety run-in phase, as described in this statistical analysis plan, will be produced when all patients in the safety run in phase either completed the study duration or discontinued from it.

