If no participants (0 of 3 DLT-evaluable participants) experience a DLT during the DLT period (4 weeks), the Randomized Phase will be initiated at this dose level. If 1 evaluable participant (1 of 3 DLT-evaluable participants) experiences DLT, then the cohort will be expanded to 6 DLT-evaluable participants. If no more DLTs are observed (1 of 6 DLT-evaluable participants), then the Randomized Phase will be initiated at the dose level tested. If 1 or more additional evaluable participants (2 of 6 DLT-evaluable participants) experiences DLT during the DLT period, a lower dose will be tested using the same 3 + 3 schema. See [Figure 5.1.2.1-1](#) for an overview of the 3 + 3 approach to be used for the Safety Run-in Phase.

Figure 5.1.2.1-1: Schematic of Safety Run-in Phase 3 + 3 Approach

Abbreviations: DLT = dose-limiting toxicity.

^a For additional details see [Section 7.4](#) (Dosage Modification).

Continuous evaluation of toxicity events will be performed. If at any time, the aggregate rate of treatment-related toxicities meeting DLT criteria exceeds 33% across participants treated in a cohort, the findings will be discussed with the Investigators and further enrollment may be interrupted. Any toxicities that occur beyond the DLT period will be accounted for in making final dose level decisions.

Generally, if a cohort is discontinued due to DLT of unclear relevance to nivolumab, a lower dose level of CDK4/6 inhibitor per product label will be tested in the next cohort. See [Section 7.4](#) (Dosage Modification) for additional details on permitted dose adjustment. If a cohort is discontinued due to DLT related to nivolumab, a different dose or dose schedule will be explored per Investigator and Medical Monitor discussion.

For cohort expansion or dose de-escalation decisions, the available toxicity information (including AEs and laboratory abnormalities that are not DLTs), clinical judgment [REDACTED] will be evaluated by the Investigators and BMS study personnel (including the Medical Monitor and statistician) during a dose decision meeting by teleconference. Drug administration at the next dose level or proceeding to the Randomized Phase must not occur until the Investigator receives written confirmation from BMS indicating that the results of the previous dose level were evaluated and that it is permissible to proceed.

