### **Schedule of Analyses:**

An analysis will be conducted when enrollment to the safety run-in phase is completed and all patients have completed at least one cycle of study treatment (1 cycle = 4 weeks) and have been followed up for an additional 4 weeks or discontinued from the study prior to that in order to support the dose selection for the randomized phase.

Final analysis will be conducted when all participants in the Randomized Phase are treated and evaluated in terms of RCB and pCR and completed the study, including the follow up phase, or discontinued from the study prior to that.

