## 6 STUDY PERIODS, TREATMENT REGIMENS AND POPULATIONS FOR ANALYSES

### 6.1 Study Periods

- Baseline period:
  - Baseline evaluations or pre-treatment events will be defined as evaluations or events that occur before the date and time of the first dose of study treatment. Evaluations (laboratory tests, pulse oximetry, vital signs [REDACTED]) on the same date and time of the first dose of study treatment will be considered as baseline evaluations. Events (AEs) on the same date and time of the first dose of study treatment will not be considered as pre-treatment events.
  - In cases where the time (onset time of event or evaluation time and dosing time) is missing or not collected, the following definitions will apply:
    - ◆ Pre-treatment AEs will be defined as AEs with an onset date prior to but not including the day of the first dose of study treatment;
    - ◆ Baseline evaluations (laboratory tests, pulse oximetry, vital signs [REDACTED]) will be defined as evaluations with a date (and time if collected) on or prior to the date of first dose of study treatment.
  - If there are multiple valid observations in the baseline period, then the latest non missing observation will be used as the baseline in the analyses. If multiple observations exist on the latest collection date (and time if collected), the record with the latest data entry date and time will be used. If multiple observations exist on the latest collection date (and time if collected) and data entry date and time, then the first observation is used as baseline, unless otherwise specified.

- ◆ Refer to the study-specific protocol for potential additional baseline evaluations definition such as baseline tumor evaluation, etc.
- Post baseline period:
  - On-treatment AEs will be defined as AEs with an onset date and time on or after the date and time of the first dose of study treatment (or with an onset date on or after the day of

first dose of study treatment if time is not collected or is missing). For subjects who are off study treatment, AEs will be included if event occurred within a safety window of 30 days (or 100 days depending on the analysis) after the last dose of study treatment. No “subtracting rule” will be applied when an AE occurs both pre-treatment and post-treatment with the same preferred term and grade.

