### **7.1.1.3 Immune-Mediated Adverse Events (US Submission)**

In order to further characterize AEs of special clinical interest, analysis of immune-mediated AEs (IMAE) will be conducted. IMAEs are specific events (or groups of PTs describing specific events) that include pneumonitis, diarrhea/colitis, hepatitis, nephritis/renal dysfunction, rash, endocrine (adrenal insufficiency, hypothyroidism/thyroiditis, hypothyroidism, thyroiditis, hyperthyroidism, diabetes mellitus, and hypophysitis), and other specific events, considered as potential immune-mediated events by investigator that meet the definition summarized below:

- those occurring within 100 days of the last dose,
- regardless of causality,
- treated with immune-modulating medication (of note, endocrine AEs such as adrenal insufficiency, hypothyroidism/thyroiditis, hypothyroidism, thyroiditis, hyperthyroidism,

diabetes mellitus, and hypophysitis are considered IMAEs regardless of immune-modulating medication use, since endocrine drug reactions are often managed without immune-modulating medication).

- with no clear alternate etiology based on investigator assessment, or with an immune-mediated component.

The list of MedDRA preferred terms used to identify IMAEs is revisited quarterly and updated accordingly. The preferred terms used for the selection at the time of the database lock by categories will be provided.

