### **7.6.8 Immune-Mediated Adverse Events (US Submission)**

IMAEs will be summarized by treatment group for each immune-mediated category / PT using the 100-day safety window:

- Overall summary of non-endocrine IMAEs by worst CTC grade (any grade, grade 3-4, grade 5) where immune modulating medication was initiated presented by Category / PT.
- Overall summary of endocrine IMAEs by worst CTC grade (any grade, grade 3-4, grade 5) presented by Category / PT.
- Overall summary of non-endocrine IMAEs leading to discontinuation by worst CTC grade (any grade, grade 3-4, grade 5) where immune modulating medication was initiated presented by Category / PT.
- Overall summary of endocrine IMAEs leading to discontinuation by worst CTC grade (any grade, grade 3-4, grade 5) presented by Category / PT.
- Overall summary of non-endocrine IMAEs leading to dose delay or reduction by worst CTC grade (any grade, grade 3-4, grade 5) where immune modulating medication was initiated presented by Category / PT
- Overall summary of endocrine IMAEs leading to dose delay or reduction by worst CTC grade (any grade, grade 3-4, grade 5) presented by Category / PT.
- Summaries of time-to onset and time-to resolution of non-endocrine IMAEs where immune modulating medication was initiated presented by Category.
- Summaries of time-to onset and time-to resolution of endocrine IMAEs presented by Category.

A by-subject listing of IMAEs will be provided. By-subject listings of time-to resolution for longest IMAEs cluster (any grade and grade 3-5 in separate summaries) will also be provided. For new studies which collect investigator assessment of potential IMAE data, a by-subject listing of AEs considered as immune-mediated events per investigator but not qualified for IMAEs definition will also be provided.

In addition, for all nivolumab treated subjects who experienced at least one IMAE, the following data presentation will be provided:

- Summary of subjects who were re-challenged with nivolumab by IMAE category, with extended follow-up.
- Summary of subjects who were re-challenged with nivolumab by IMAE category, with extended follow-up.

For these, re-challenge is considered to have occurred when last nivolumab infusion was administered after the onset of an IMAE.

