### **7.6.10 Adverse Events of pneumonitis and lung disease**

The following adverse events will be summarized by treatment group:

- Interstitial Lung Disease
- Pneumonitis
- Immune-Mediated Pneumonitis

The following analyses will be conducted using the 100-day safety window:

- Overall summary by worst CTC grade (any grade, grade 3-4, grade 5) presented by Category / PT

A by-subject listing will be provided.

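### SAP 7.10 summarises IMAEs, OEOSI and ILD/pneumonitis for the dose decision on a 30-day window, although the rest of the SAP puts the same events on 100 days

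*SAP*

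**What the plan says.** SAP 7.10 lists what will be produced when the dose for the Randomized Phase is chosen. One item runs together SAEs, discontinuations, dose modifications, all AEs, select AEs, IMAEs, OEOSI and the ILD/pneumonitis group. It ends: "All these summaries will be presented by worst CTC grade (any grade, grade 3-4, grade 5) using the 30 days safety window". No reason is given for that window. The section opens by saying that all available run-in data will be used.

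Elsewhere the SAP treats three of these groups differently:

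- **IMAEs, definition (7.1.1.3):** the qualifying events are "those occurring within 100 days of the last dose".
- **IMAEs, summaries (7.6.8):** "IMAEs will be summarized by treatment group for each immune-mediated category / PT using the 100-day safety window".
- **OEOSI (7.6.9) and ILD, pneumonitis and immune-mediated pneumonitis (7.6.10):** "The following analyses will be conducted using the 100-day safety window".

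SAP 6.1 explains how a window acts: "AEs will be included if event occurred within a safety window of 30 days (or 100 days depending on the analysis"). The limit concerns only people who have stopped study drug and is counted from their final dose. Participants still on treatment are not limited.

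On endocrine events, 7.1.1.3 says that they "are considered IMAEs regardless of immune-modulating medication use". The 7.10 item names non-endocrine and endocrine IMAEs together and then adds the condition that immune-modulating medication was started.

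**The concern.** The run-in tables would not match the SAP's own account of these events. For IMAEs the mismatch goes beyond presentation: a 30-day table counts only part of an event defined on 100 days. A pneumonitis on day 45 after last dose would be absent from the ILD/pneumonitis summary at the dose decision and present in the CSR table for the same participant.

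The participants exposed to this are those who have stopped. Protocol 5.1.2.1 requires study treatment to stop after a drug-related event meeting DLT criteria, and protocol 8.1.1 stops all study drugs when nivolumab is discontinued. Their later data are collected: protocol Table 2-3 documents AEs in the run-in cohorts for at least 100 days after last nivolumab.

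The setting makes a clean table worth having. Revised Protocol 03 added a baseline chest X-ray and pulse oximetry to watch for ILD/pneumonitis with the palbociclib combination. Protocol 5.1.2.1 also says: "Any toxicities that occur beyond the DLT period will be accounted for in making final dose level decisions". A zero row in a summary table is easily read as no events observed.

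**Working it through.** The plan states no figure to reproduce here, so the check is a comparison of text followed by day counting.

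**Windows side by side**

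| Event group | SAP 7.10 | Elsewhere in the SAP |
|---|---|---|
| IMAEs | 30 days | 100 days (7.1.1.3 definition; 7.6.8 summaries) |
| OEOSI | 30 days | 100 days (7.6.9 summaries) |
| ILD/pneumonitis | 30 days | 100 days (7.6.10 summaries) |

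The mismatch holds for all three groups. Only for IMAEs is 100 days part of the definition; for the other two it is the summary window.

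**Timing of the cut.** The SAP's Schedule of Analyses requires that "all patients have completed at least one cycle of study treatment (1 cycle = 4 weeks") and have a further 4 weeks of follow-up, unless they left the study sooner. For the last participant enrolled, the earliest cut is therefore 28 + 28 = day 56.

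**Observed time dropped.** With last dose of any study drug on day L and the cut on day F:

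dropped days = max(0, min(F, L + 100) − (L + 30))

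At F = 56, L + 100 always lies beyond the cut, so this reduces to max(0, 56 − (L + 30)). It is zero once L reaches 56 − 30 = 26.

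| Last dose L | L + 30 | Dropped, F = 56 | F = 84 | F = 112 | F = 140 |
|---|---|---|---|---|---|
| 1 | 31 | 25 | 53 | 70 | 70 |
| 10 | 40 | 16 | 44 | 70 | 70 |
| 21 | 51 | 5 | 33 | 61 | 70 |
| 26 | 56 | 0 | 28 | 56 | 70 |
| 28 | 58 | 0 | 26 | 54 | 70 |

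The last-dose days are examples. The cuts at days 84, 112 and 140 are illustrative assumptions for participants enrolled earlier, because the documents give no accrual rate. The ceiling is 100 − 30 = 70 days. For someone who left the study early, F becomes the last observed day and the loss is smaller.

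**Endocrine wording.** SAP 7.6.8 has separate lines: the non-endocrine summaries carry the medication condition and the endocrine summaries do not. SAP 7.10 merges the two with the condition at the end, so it can be read as covering both.

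**The case against.** The case that this matters little is substantial, and most of it stands.

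- **The events are not hidden.** SAP 7.10 also provides a listing of AEs with no stated window, and summaries and listings of deaths and DLTs. SAEs reach the sponsor within 24 hours (protocol 9.2.1). With 3 to 6 participants per dose level, a by-subject listing can be read in full. A reader might infer that those choosing the dose would be blind to late lung or immune events; the documents do not support that.
- **The tables do not open randomisation.** Protocol 5.1.2.1 uses a 3+3 rule and a dose decision meeting that weighs all available toxicity information with clinical judgment. The SAP analysis supports that decision. Nor does the protocol sentence on toxicities after the DLT period require a summary table, so 7.10 does not breach it.
- **A dropped event cannot change the 3+3 count.** It is tempting to say that one event is 1/6 to 1/3 (17–33%) of a level and could tip the decision. But an event more than 30 days after last dose falls on day 32 or later, outside the 4-week DLT period. It enters only through continuous toxicity evaluation and judgment, neither of which is tied to these tables.
- **The SAP allows the window to vary by analysis, and this is an early cut.** Section 6.1 says so, and 7.10 promises the full set of analyses for the CSR. That permits a choice but does not explain it. Incomplete follow-up at the cut is a reason for a footnote; it is not a reason to omit events already recorded.
- **The endocrine item may be shorthand.** It may simply compress the two lines of 7.6.8, and endocrine events also appear under select AEs and all AEs. It is ambiguous; a reading that it plainly excludes untreated endocrine IMAEs goes too far.

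The documents also give no figure for how often early stopping would be due to toxicity, so no frequency can be attached to the problem.

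**Conclusion.** The inconsistency is real and confined to three sets of summary tables. As written, 7.10 would leave out IMAEs, OEOSI and ILD/pneumonitis events already observed more than 30 days after last dose, and for IMAEs would tabulate only part of the defined event. The same participants' events would then surface in the CSR tables.

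The size is modest. No one still on treatment, or within 30 days of last dose at the cut, is affected. For the last participant enrolled, only a last dose before day 26 matters at a day-56 cut, and the loss is at most 25 days. Losses towards 70 days require longer follow-up, as for earlier enrollees or a previous dose level. They rest on assumed cut dates and on AE recording up to 100 days after the last dose.

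The point supports correcting the tables so that they agree with the SAP's own definitions. It does not support a claim that the dose decision would be made without sight of these events.

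**What to change.** In SAP 7.10:

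1. Use the 100-day window for the IMAE, OEOSI and ILD/pneumonitis summaries, or show the 30-day and 100-day versions together. Keep 30 days for the other summaries.
2. Split the IMAE item in two, so that the immune-modulating-medication condition applies to non-endocrine IMAEs only, as in 7.1.1.3 and 7.6.8.
3. Footnote the 100-day tables to say that follow-up is incomplete at the cut, and give the number of participants off treatment with less than 100 days observed.

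If 30 days is intended for these groups, 7.10 should say why and point the reader to the AE listing for later events.

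The cost is a SAP wording change and a few extra table runs. The 100-day summaries are already specified for the CSR, and the protocol already collects the AE data. No visit, sample size or dose rule changes. The one drawback is an incomplete 100-day table at an early cut, which the footnote covers.

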## 8 CONVENTIONS

The following conventions may be used for imputing partial dates for analyses requiring dates:

- For missing and partial adverse event onset dates, imputation will be performed using the Adverse Event Domain Requirements Specification
- For missing and partial adverse event resolution dates, imputation will be performed as follows (these conventions may change):
  - If only the day of the month is missing, the last day of the month will be used to replace the missing day. If the imputed date is after the death date or the last known alive date, then the latest known alive date or death date is considered as the resolution date.
  - If the day and month are missing or a date is completely missing, it will be considered as missing.
- Missing and partial non-study medication domain dates will be imputed using the derivation algorithm described in 4.1.3 of BMS Non-Study Medication Domain Requirements Specification.
- Missing and partial radiotherapy and surgery dates will be imputed using algorithm described in [APPENDIX 2](#).
- For death dates, the following conventions will be used for imputing partial dates:
  - If only the day of the month is missing, the 1st of the month will be used to replace the missing day. The imputed date will be compared to the last known alive date and the maximum will be considered as the death date.
  - If the month or the year is missing, the death date will be imputed as the last known alive date.
  - If the date is completely missing but the reason for death is present, the death date will be imputed as the last known date alive.
- For date of progression after start of study therapy, the following conventions will be used for imputing partial dates:
  - If only the day of the month is missing, the 1st of the month will be used to replace the missing day. In case of the date of death is present and complete, the imputed progression

date will be compared to the date of death. The minimum of the imputed progression date and date of death will be considered as the date of progression.

- If the day and month are missing or a date is completely missing, it will be considered as missing.
- For date of progression to prior therapies, the following conventions will be used for imputing partial dates:
  - If only the day of the month is missing, the 1st of the month will be used to replace the missing day.
  - If the day and month are missing or a date is completely missing, it will be considered as missing.
- For other partial/missing dates, the following conventions were used:
  - If only the day of the month is missing, the 15th of the month will be used to replace the missing day.
  - If both the day and the month are missing, “July 1” will be used to replace the missing information.
  - If a date is completely missing, it will be considered as missing.

The following conversion factors will be used to convert days to months or years:

$$1 \text{ month} = 30.4375 \text{ days and } 1 \text{ year} = 365.25 \text{ days.}$$

Duration (e.g. time-to onset, time-to resolution) will be calculated as follows:

$$\text{Duration} = (\text{Last date} - \text{first date} + 1)$$

Last known alive date will be defined based on all appropriate dates collected on the CRF.

All statistical analyses will be carried out using SAS (Statistical Analysis System software, SAS Institute, North Carolina, USA) unless otherwise noted.

